Participant participation will include screening, treatment, and follow-up. Screening will last up to 30 days before first dose of study treatment, during which time the participant's eligibility and baseline characteristics will be determined. Participants will receive study treatment per the dose schedule in [Table 1](#). No cross-over between arms is allowed. Study treatment may be continued until disease progression (including treatment failure by International Working Group [IWG] 2006 criteria or relapse after partial/complete remission [PR/CR]), loss of clinical benefit, or unacceptable toxicities occur. In case participants discontinue the study treatment due to reasons other than disease progression, participants will be followed up for response assessments until documented disease progression occurs. For participants who come off the study treatment to receive an SCT, follow-up for response assessment and collection of SOC bone marrow biopsy/aspirate results will continue until documented disease progression occurs or start of new anticancer therapy, whichever occurs first. The participants will be followed for survival, unless the participant explicitly indicates a desire to forego survival follow-up in writing to their study investigator, until death, withdrawal of consent, loss to follow-up, or study termination, whichever occurs first. For any participant who dies during this follow-up period, the immediate cause of death must be reported to the Sponsor. For participants who are lost to follow-up or withdraw consent, study staff may use public records (eg, public health records) to obtain information about survival status where allowable by local regulation.

Table 1. Dose Level and Schedule

Treatment Arms	Drug/Dose/Route	Dose Schedule (Day per 28-day Cycle)		
		Cycle 1	Cycle 2	Cycle 3+
Experimental arm (Magrolimab+ azacitidine) And Control arm (azacitidine + placebo)	Azacitidine 75 mg/m ² SC or IV ^a	Days 1–7 or Days 1–5 and 8–9	Days 1–7 or Days 1–5 and 8–9	Days 1–7 or Days 1–5 and 8–9
Treatment Arms	Drug/Dose/Route	Dose Schedule		
		Priming Dose		Maintenance Dose
Experimental arm (Magrolimab+ azacitidine)	Magrolimab 1 mg/kg IV	Days 1, 4		
	Magrolimab 15 mg/kg IV	Day 8		
	Magrolimab 30 mg/kg IV	Days 11, 15, followed by weekly administration for 5 doses (Days 22, 29, 36, 43, 50)		
Control arm (azacitidine + placebo)	Placebo	to mirror the magrolimab dosing schedule above		to mirror the magrolimab dosing schedule above

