Visit Window	End-of-treatment Visit	Safety Follow-up Visit/Call (Telephone) ^a		Long-term Follow-up	Survival Follow-up
	Within 7 Days after Last Dose or EOT Decision	30 Days after Last Dose	70 Days after Last Dose ^k	Until Start of New Anticancer Therapy or Transformation to AML ^b	Every 2 Months Until Death or End of Study
	± 7 Days	± 7 Days	± 7 Days	+4 Weeks	
Serum or urine pregnancy test	X			Q4W ^c	Q4W ^c
CBC with differential, platelet count, reticulocytes	X			Q8W ^d	
Serum or plasma chemistry	X				
Peripheral blood for biomarker studies	X				
Pharmacokinetics	X				
Antidrug antibodies	X				
Bone marrow biopsy and aspirate for MRD monitoring and cytogenetics ^{d,e}	X			Q8W ^d	
Response assessment ^{e,f}	X			Q8W ^d	
ECOG	X				
Vital signs	X				
Symptom-directed physical examination	X				
PRO assessment ^g	X			X	
Adverse events ^h	X	X	X		
Concomitant medications	X	X	X		
Blood transfusion ⁱ				X	X
New anticancer therapy ^j				X	X
Survival follow-up					Q2M

Abbreviations: AE = adverse event; AML = acute myeloid leukemia; CBC = complete blood count; CR = complete remission; eCRF = electronic case report form; EOT = end of treatment; EQ-5D-5L = 5-level EuroQol 5 dimensions; FACT-Anemia = Functional Assessment of Cancer Therapy-Anemia; IWG = International Working Group;

MDS = myelodysplastic syndrome; MRD = minimal residual disease; PGIC = Patient Global Impression of Change; PGIS = Patient Global Impression of Severity; PR = partial remission; PRO = patient-reported outcome; QxM = every x months; QxW = every x weeks; SAE = serious adverse event.

- a If the participant experiences a treatment-related AE or an SAE (regardless of attribution), the participant must be asked to come to the site.
- b Until start of new anticancer therapy or transformation to AML, whichever comes first.
- c Collect until the end of the contraception requirement.
- d Bone marrow assessment, MRD, CBC, and response assessment should be performed until start of new anticancer therapy or transformation to AML, whichever comes first. Conventional cytogenetic testing (per institutional standards) is required for all participants.
- e For participants who come off the study treatment to undergo a stem cell transplant, response assessments for relapse/remission status and bone marrow aspirate results are required to be obtained locally and entered into the eCRF.

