- f Response assessment at EOT visit not required if performed within the last 30 days or progressive disease has been documented. After disease progression (including treatment failure by IWG criteria and relapse after CR or PR), response assessment will focus on evaluation of transformation to AML.
- g Paper PROs will be administered in this study: The FACT-Anemia questionnaire, the EQ-5D-5L, the PGIS, and the PGIC will be administered. The participant should complete these questionnaires before other study procedures at required visits. FACT-Anemia and EQ-5D-5L should be implemented prior to PGIS/PGIC. FACT-Anemia, EQ-5D-5L, the PGIS, and the PGIC should also be collected during long-term follow-up prior to initiation disease progression or initiation of a new anticancer therapy.
- h Report all AEs through the Safety Follow-up Visit/Call and any treatment-related SAEs thereafter.
- i Collect blood transfusions until start of new anticancer therapy.
- j Collect new anticancer therapy data following the last dose of study treatment.
- k For participants who do not initiate new anticancer therapy after the last dose. See Section [5.1.10](#) for adverse event reporting details.

Table 6. Schedule of Assessments - Repriming (Required After > 4 Weeks Have Lapsed Since the Last Dose of Magrolimab/Placebo Delays)

Visit Window (Days)	Day										
	1	2	3	4	5	6	7	8	11	15	22
	-	-	± 3	± 3	± 3	± 3	± 3	± 3	± 3	± 3	± 3
Pregnancy test	X										
CBC with differential, platelets, and reticulocytes ^{a,b}	X	X		X				X	X	X	X
Haptoglobin and LDH	X							X			
Serum or plasma chemistry ^a	X							X		X	X
Peripheral smear ^{a,c}	X	X							X		
Peripheral blood for biomarker studies ^d	X							X			
PK ^d	X							X			
Antidrug antibodies ^a	X										
Vital signs ^c	X	X						X		X	X
Symptom-directed physical examination ^a	X							X		X	
Adverse events	X	X	X	X	X	X	X	X	X	X	X
Concomitant medications	X	X	X	X	X	X	X	X	X	X	X
Blood transfusions	X	X	X	X	X	X	X	X	X	X	X
Premedication ^f	X			X				X	X		
Magrolimab/placebo: repriming ^g	X			X				X	X	X	X

Abbreviations: CBC = complete blood count; ECOG = Eastern Cooperative Oncology Group; LDH = lactate dehydrogenase; PK = pharmacokinetic(s); PRO = patient-reported outcome; WBC = white blood cell.

a Pretreatment assessments are to be collected within 24 hours prior to study treatment administration.

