5.1.8. Bone Marrow Assessments

Bone marrow assessments (including aspirate and core/trephine biopsy) are required for response assessments (refer to Section 5.3 and Appendix B), including conventional cytogenetic analysis per institutional standards. In addition, bone marrow specimens may be used for biomarker studies, MRD monitoring, CCI, and biobanking. Minimal residual disease testing will be performed by a central laboratory. Bone marrow aspirate slides for response assessment will also be sent to a central laboratory. Details for preparation and distribution of aspirate and biopsy/trephine specimens to the testing laboratories will be provided in the Laboratory Manual for this study.

Bone marrow assessments include collection of both aspirate and core biopsy (trephine) specimens at each time point according to the schedules of assessments in Section 4.3.

Bone marrow biopsies for response assessments may be adjusted by ± 1 week for Cycle 3 Day 1. After Cycle 3 Day 1, the window is ± 14 days.

Response assessment at End-of-Treatment (EOT) Visit is not required if performed within the last 30 days or progressive disease has been documented. Bone marrow response assessments should continue during long-term follow-up approximately every 8 weeks until transformation to AML is documented or start of new anticancer therapy, whichever comes first. For participants who come off the study treatment to receive an SCT, follow-up for response assessment and collection of SOC bone marrow biopsy/aspirate results will continue until documented relapse or progressive disease occurs. After documented relapse or progressive disease, follow-up for response assessment and collection of SOC bone marrow biopsy/aspirate results will continue until transformation to AML occurs or start of new anticancer therapy, whichever comes first.

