Although disease progression (including treatment failure by IWG criteria or relapse after PR/CR) is considered a sufficient reason for discontinuing a participant from study treatment, given the delayed treatment benefit commonly seen in immune therapies, the Investigator is advised to continue to treat the participant until the confirmation of disease progression through a subsequent response assessment at least 4 weeks apart (i.e., disease worsening compared with the previous assessment), or until the Investigator considers the study treatment to be no longer clinically beneficial to the participant or the change of disease state renders the participant unacceptable for further treatment in the judgment of the Investigator. All participants must be followed through completion of all study treatment.

Participants who discontinue study treatment are to return for an EOT Visit for evaluation of safety within 7 days of their last dose or the decision to end study treatment. In addition, participants are to have Safety Follow-up telephone calls 30 days (± 7 days) after their last dose of study treatment. Participants are also to have Safety Follow-up telephone calls 70 days (± 7 days) after their last dose of study treatment or initiation of new anticancer therapy, whichever is earlier. When a serious AE (SAE) or treatment-related AE is reported during the telephone call, the participant should come to the clinic for physical examination and blood tests, if clinically needed. Follow-up for ongoing SAEs or treatment-related AEs after the Safety Follow-up Visit/Call will stop if a participant begins another anticancer therapy.

All participants who discontinue study treatment will participate in long-term follow-up for disease response until documented transformation to AML or start of new anticancer therapy, whichever occurs first, unless the participant withdraws consent for such follow-up or withdraws completely from the study (Section 5.7.2).

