1.2. Study Design

This is a Phase 3, randomized, double-blind, placebo-controlled multicenter study investigating magrolimab + azacitidine compared with azacitidine + placebo in previously untreated patients with intermediate/high/very high risk MDS by IPSS-R. The primary endpoints are CR rate and OS. Patients will be randomized in 1:1 ratio to receive either magrolimab + azacitidine (experimental arm) or azacitidine + placebo (control arm). Randomization will be stratified by 3 factors: 1) geographic region (US versus ex-US sites); 2) cytogenetic risk status (very good/good/intermediate versus poor/very poor versus unknown) according to IPSS-R {Greenberg 2012}; and 3) percentage of bone marrow blasts ($\geq 10\%$ versus < 10% blasts).

The primary analysis of CR rate will be conducted 8 months after 348 patients are randomized. Patient participation will include screening, treatment, and follow-up. Screening will last up to 30 days before the first dose of study treatment, during which time the patient's eligibility and baseline characteristics will be determined. Patients will receive study treatment per the dose schedule in Table 1-1. No cross-over between arms is allowed. Study treatment may be continued until disease progression (including treatment failure by International Working Group [IWG] 2006 criteria or relapse after partial/complete remission [PR/CR]), loss of clinical benefit, or unacceptable toxicities occur. In case patients discontinue the study treatment due to reasons other than disease progression, patients will be followed up for response assessments until documented disease progression occurs. For patients who come off the study treatment to receive a stem cell transplant (SCT), follow-up for response assessment and collection of SOC bone marrow biopsy/aspirate results will continue until documented disease progression occurs or start of new anticancer therapy (excluding SCT), whichever occurs first. All participants will be followed for survival until death, withdrawal of consent, or the end of the study, whichever occurs first. For participants who are lost to follow-up or withdraw consent, study staff may use public records (eg, public health records) to obtain information about survival status where allowable by local regulation.

The study treatments within each arm are described in Table 1-1:

		Dose Sche	dule (Day pe	r 28-day Cycle)
Treatment Arms	Drug/Dose/Route	Cycle 1	Cycle 2	Cycle 3+

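### For two groups of participants, Protocol 4.1 and SAP 1.2 end response assessments at progression, while Table 5 and Section 5 continue them to AML; a site following 4.1 would miss later transformations

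*Protocol*

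**What the plan says.** Protocol 4.1 gives an end of response follow-up for two groups.

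- Treatment stopped for reasons other than progression: "participants will be followed up for response assessments until documented disease progression occurs". SAP 1.2 has the same rule: "patients will be followed up for response assessments until documented disease progression occurs".
- Treatment stopped to receive SCT: response assessment and collection of marrow "results will continue until documented disease progression occurs or start of new anticancer therapy, whichever occurs first". SAP 1.2 matches this, but adds that SCT itself is not counted as new anticancer therapy.

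For participants who stop because of progression, 4.1 gives no rule on response follow-up.

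The schedule and procedural sections give a different end point.

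- Table 5, footnote d: "response assessment should be performed until start of new anticancer therapy or transformation to AML, whichever comes first". Footnote b sets the same end for long-term follow-up. Footnote f says that after progression "response assessment will focus on evaluation of transformation to AML".
- Section 5.1.8: marrow response assessments continue "approximately every 8 weeks until transformation to AML is documented or start of new anticancer therapy, whichever comes first". Section 5.3 agrees.
- Section 5.7.1: everyone who discontinues treatment enters "long-term follow-up for disease response until documented transformation to AML or start of new anticancer therapy".
- SCT participants, Section 5.1.8: "After documented relapse or progressive disease, follow-up for response assessment and collection of SOC bone marrow biopsy/aspirate results will continue until transformation to AML" or new anticancer therapy. Sections 5.3 and 5.7.1 agree.
- SAP Appendix Table 4 reproduces footnotes b, d and f of Table 5, so the SAP also disagrees with its own Section 1.2.

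**The concern.** Transformation to AML is one of the two components of EFS and the only event in time to transformation to AML. These are third and sixth in the ordered list of key secondary endpoints (Protocol 8.3.1, SAP 2.1). Protocol 8.4 dates transformation by the collection of the marrow sample that led to the diagnosis, so ascertainment depends on marrows being taken.

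Progression in Protocol Table 19 can be documented well short of leukemia. Examples are a blast rise from below 5% to above 5%, a fall in granulocytes or platelets, or transfusion dependence. If assessments stop there, the marrow that would show a later transformation is never scheduled.

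**Working it through.** No arithmetic applies. The check sets the rules side by side and follows one participant through each.

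| Group | Protocol 4.1 and SAP 1.2 | Table 5, 5.1.8, 5.3, 5.7.1, SAP Appendix Table 4 | Conflict? |
|---|---|---|---|
| Stopped for a reason other than progression or SCT | Ends at progression | Ends at AML or new anticancer therapy | Yes |
| Stopped for SCT | Ends at progression or new anticancer therapy | Continues past relapse or progression, to AML or new anticancer therapy | Yes |
| Stopped because of progression | No rule given | Ends at AML or new anticancer therapy | No; 4.1 is silent |

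Take a participant who stops for toxicity, later progresses through a blast rise that stays below leukemia, and transforms some months after that without having started new therapy.

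1. *Under Table 5.* A marrow is due about every 8 weeks after progression. The transformation is found, and its date is an event for both EFS and time to AML.
2. *Under 4.1, time to AML.* No marrow is due after progression, so no sample dates the transformation. SAP 6.2.1 and Table 6-2 censor at the last response assessment, which is about the progression visit. A participant who has just progressed is plausibly at higher risk of AML than one still under assessment, so this censoring is plausibly informative.
3. *Under 4.1, EFS.* The AML date is lost. Survival follow-up continues, so a later death is still an event, but at a later date. By the censoring rule in SAP 6.2.1, this holds only if no new anticancer therapy other than SCT started before the death.
4. *Not affected.* AML found at the progression assessment itself is captured under either rule. PFS has already had its event. CR rate and OS do not depend on marrows taken after progression.

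A second ambiguity concerns SCT. Table 5 footnotes b and d end assessments at new anticancer therapy without excepting SCT, and elsewhere the protocol counts SCT as new anticancer therapy (5.1.10, 8.4). Yet 5.1.8 requires follow-up after SCT, Table 5 footnote e asks for response and marrow results in SCT participants, and SAP 6.2.1 includes transformations after SCT and does not censor at SCT. The intent is clear from these places, but neither 4.1 nor footnotes b and d state it.

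**The case against.** The strongest reply is that 4.1 is a design overview. It sends the reader to Section 4.3 for the schedules, and Section 5 says that assessments follow Section 4.3. Table 5 and three procedural sections all carry assessments on to AML, and 5.9 lists follow-up for AML separately from progression. For SCT participants, 4.1 can be read as the first stage of the two-stage rule in 5.1.8. SAP 1.2 describes the design and does not govern site visits. Much of this stands: a site working from Table 5 collects the right data, and loss occurs only where a site follows 4.1. It does not remove the contradiction, because 4.1 states an end point and does not say that follow-up for AML continues after it.

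It is also fair that the key secondary endpoints are tested only if OS and every earlier endpoint in the order succeed.

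Three stronger readings are tempting, and the documents do not support them.

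- *That 4.1 ends assessments at progression for everyone.* Its two sentences cover only the groups in the first two rows of the table.
- *That the loss can be counted.* A reader might apply the 25% chance of leukemic transformation in Protocol 2.1.1 to all 520 participants (0.25 × 520 = 130) and take a share of that. The 25% is background with no time horizon. The documents give no rate of transformation after progression, and 520 is not the number in the two groups. New anticancer therapy, which ends assessment under Table 5 as well, would have to be subtracted.
- *That one arm would be favoured.* This would need different progression rates or site practice by arm, and neither is shown.

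**Conclusion.** The plan is wrong as written: for the two named groups, Protocol 4.1 and SAP 1.2 contradict Table 5, Sections 5.1.8, 5.3 and 5.7.1, and SAP Appendix Table 4. The consequence is conditional on a site following 4.1. Transformations after progression would then go unrecorded, with plausibly informative censoring of time to AML and a lost or delayed event in EFS. The size cannot be estimated from the documents. The point rests on the text alone and on one assumption, that some participants in these groups progress before they transform, which the Table 19 definition of progression allows. It is a modest point about two key secondary endpoints.

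**What to change.** In Protocol 4.1 and SAP 1.2, replace the stop at progression with the rule already in Table 5, 5.1.8, 5.3 and 5.7.1: response assessments continue until transformation to AML or start of new anticancer therapy, whichever is first. State in 4.1 and in Table 5 that SCT does not end these assessments, in line with 5.1.8 and the SAP censoring rule, and carry the same note into SAP Appendix Table 4.

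The cost is a few sentences in the two documents. No visit, procedure or data item is added beyond what Table 5 already requires. An AML question at the 2-monthly survival contact is not needed for this correction, and a date obtained without a marrow sample might not meet the definition in Protocol 8.4.

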4.2. Study Schematic

The study schematic is presented in Figure 4.

Figure 4.

Study 5F9009 Schematic

Magrolimab (or saline placebo) dosing:

Priming Dose:

- 1 mg/kg on Days 1 and 4
- 15 mg/kg on Day 8
- 30 mg/kg Days 11, 15
- 30 mg/kg weekly for 5 doses (Days 22, 29, 36, 43, 50)

Maintenance Dose:

- 30 mg/kg on Day 57 and 30 mg/kg every 2 weeks thereafter

Azacitidine dosing:

- 75 mg/m² IV or SC Days 1-7 (or Days 1-5 and 8-9) every 28-day cycle

Abbreviations: CR= complete remission; IPSS-R = Revised International Prognostic Scoring System; IV= intravenous; MDS=myelodysplastic syndrome; OS = overall survival; SC=subcutaneous

4.3. Schedule of Assessments

The schedule of assessments is presented in a separate table for each study period: screening ([Table 2](#)), treatment period- azacitidine dosing and study assessments ([Table 3](#)), treatment period-magrolimab or placebo dosing and study assessments ([Table 4](#)), posttreatment ([Table 5](#)), and repriming ([Table 6](#)). A cycle is 28 days long.

Table 2. Schedule of Assessments - Screening

Assessment	Study 5F9009
	Day -30 to -1
Informed consent	X ^a
Demographics	X
Medical and cancer history	X
Pregnancy test	X ^b
Serum or plasma chemistry	X
Serum uric acid, phosphorus	X
Hematology ^d	X
Blood phenotyping or genotyping, type, screen (ABO/Rh), DAT ^e	X
Urinalysis	X
Bone marrow biopsy and aspirate for blast evaluation, biomarker studies, cytogenetics, and MRD assessment ^c	X
ECOG	X
Vital signs, height, and weight	X
Complete physical examination	X
ECG (single)	X
Hepatitis B, hepatitis C, and HIV ^f	X
Adverse events related to protocol-mandated procedures	X
Concomitant medications	X
Entry criteria	X
Randomization	X ^a

Abbreviations: ABO = any of the 4 blood groups A, B, AB, and O comprising the ABO system; DAT = direct antiglobulin test; ECG = electrocardiogram; ECOG = Eastern Cooperative Oncology Group; FSH = follicle-stimulating hormone; MRD = minimal residual disease; RBC = red blood cell; Rh = Rhesus factor; SOC = standard of care.

- a Screening must be completed before randomization. Randomization must occur within 30 days of signing informed consent. The first dose of study treatment (Table 3 and Table 4) must be given within 72 hours after randomization.
- b Screening pregnancy test may be used as the Day 1 test if performed within 72 hours of first dose; additional guidance is provided in Section 5.1.1. FSH test is required for female participants who are < 54 years old who are not on hormonal contraception and who have stopped menstruating for ≥ 12 months but do not have documentation of ovarian hormonal failure.
- c A trephine (biopsy) is to be collected for baseline. A bone marrow biopsy collected per SOC within 30 days of randomization can be considered the screening sample, and shipped to central laboratory. This procedure must be performed prior to the first dose of study treatment at the latest. An aspirate sample must be collected at the screening visit for blast evaluation, MRD assessment, biomarker studies, baseline for response assessment and biobanking. It is preferred that bone marrow aspirate samples are obtained at the time of bone marrow (trephine) biopsy. Conventional cytogenetics to be tested per institutional standards.
- d Hematology analytes to be assessed at screening are provided in Table 7.
- e ABO/Rh type, antibody screen, DAT, and extended RBC phenotyping (including minor antigens such as CcDEe, Cw, MNSs, Kk, FyaFyb, and JkaJkb) must be performed for each participant. Red blood cell genotyping instead of extended RBC phenotyping is acceptable for any patient. Red blood cell genotyping (instead of an extended RBC phenotyping) must be performed if a participant received any RBC or whole blood transfusion within the previous 3 months (unless the laboratory has availability for special techniques for performing phenotyping for participants with a recent transfusion). Results must be available before the first dose of magrolimab.
- f Refer to Exclusion Criteria 13 and Other Laboratory Measurements in Table 7.

Table 3. Schedule of Assessments - Treatment Period-Azacitidine Dosing and Study Assessments

Visit Window (Days)	Cycle (28-day Cycles)																					
	1							2							3+							
	None		± 3					± 3							± 3							
Cycle Day	1	2	3	4	5	6	7	1	2	3	4	5	6	7	1	2	3	4	5	6	7	
PRO assessment ^a	X							X							X							
CBC with differential, platelets, reticulocytes ^b	X							X							X							
Serum or plasma chemistry ^b	X							X							X							
Bone marrow biopsy and aspirate for biomarker studies ^c															X ^{d,e}							
Bone marrow aspirate biopsy for MRD monitoring, cytogenetics, and response assessment ^{d,f}															X Q2C, Q3C ^e							
Vital signs ^g	X	X	X	X	X	X	X	X	X	X	X	X	X	X	X	X	X	X	X	X	X	X
Symptom-directed physical examination ^b	X							X							X							
Adverse events	X	X	X	X	X	X	X	X	X	X	X	X	X	X	X	X	X	X	X	X	X	X
Blood transfusion	X	X	X	X	X	X	X	X	X	X	X	X	X	X	X	X	X	X	X	X	X	X
Concomitant medications	X	X	X	X	X	X	X	X	X	X	X	X	X	X	X	X	X	X	X	X	X	X
Azacitidine ^h	X	X	X	X	X	X	X	X	X	X	X	X	X	X	X	X	X	X	X	X	X	X

Abbreviations: CBC = complete blood count; EQ-5D-5L = 5-level EuroQol 5 dimensions; FACT-Anemia = Functional Assessment of Cancer Therapy-Anemia; MRD = minimal residual disease; PGIC = Patient Global Impression of Change; PGIS = Patient Global Impression of Severity; PRO = patient-reported outcome; Q2C = every 2 cycles; Q3C = every 3 cycles.

- a Four PRO questionnaires will be administered in this study: the FACT-Anemia questionnaire, the EQ-5D-5L, the PGIS, and the PGIC. The participant should complete these questionnaires before other study procedures at required visits. No PGIC assessment at Cycle 1 Day 1. FACT-Anemia and EQ-5D-5L should be implemented prior to PGIS/PGIC.
- b If magrolimab and azacitidine are administered on the same day, only one such study assessment is needed. Assessments should be performed prior to study treatment administration. Pretreatment assessments for the initial dose (Cycle 1 Day 1) may be collected up to 72 hours before administration of study treatment; thereafter, pretreatment assessments are to be collected within 24 hours prior to study treatment administration.
- c Bone marrow biopsy samples will be collected at Day 1 of Cycles 3 and 10.
- d An aspirate sample will be collected for response assessment, biomarker studies, and MRD assessment. Conventional cytogenetics to be tested per institutional standards. Response assessments may be adjusted by ± 1 week for Cycle 3 Day 1. After Cycle 3 Day 1, the window is ± 14 days.
- e An aspirate sample will be collected for biomarker studies at Day 1 of Cycles 3, 5, 7, 10, and 13.
- f Samples will be collected at Day 1 of Cycles 3, 5, and 7 and then every 3 cycles thereafter during study treatment. Bone marrow aspirate biopsies for response assessments may be adjusted by ± 1 week for Cycle 3 Day 1. After Cycle 3 Day 1, the window is ± 14 days.
- g Vital signs will be assessed prior to infusion/injection of each study treatment. Weight will be assessed on Day 1 of each cycle. Details are provided in Section 5.1.5.
- h If azacitidine and magrolimab/placebo are administered on the same day, azacitidine administration should be completed at least 1 hour before magrolimab/placebo administration. Azacitidine may be administered on an alternative schedule of Days 1 to 5, Day 8, and Day 9 of a 28-day cycle for flexibility and convenience.

Table 4. Schedule of Assessments - Treatment Period-Magrolimab or Placebo Dosing and Study Assessments

Dose Schedule	Priming Dosing											Maintenance Dosing	
	None		± 3									± 3	
Visit Window (Days)	1	2	4	8	11	15	22	29	36	43	50	57	every 2 Weeks thereafter
Pregnancy test ^a	X							X				X Q4W	
CBC with differential, platelets, reticulocytes ^{b,c,d}	X ^e	X	X ^e	X	X	X	X	X	X	X	X	X	X
Haptoglobin and LDH ^c	X			X				X					
Serum or plasma chemistry ^{b,c}	X			X		X	X	X		X		X	X
Peripheral smear ^{c,f}	X	X			X								
Peripheral blood sample for biomarker studies ^g	X			X				X				X ^h	
PK ^g	X			X				X				X ⁱ	
Antidrug antibodies ^{c,j}	X							X				X ⁱ	
Vital signs ^k	X		X	X	X	X	X	X	X	X	X	X	X
Symptom-directed physical examination ^{b,c}	X			X		X		X				X	X
Adverse events	X	X	X	X	X	X	X	X	X	X	X	X	X
Blood transfusion	X	X	X	X	X	X	X	X	X	X	X	X	X
Concomitant medications	X	X	X	X	X	X	X	X	X	X	X	X	X
Premedication ^l	X		X	X	X								
Magrolimab or placebo ^m	X ⁿ		X ⁿ	X	X	X	X	X	X	X	X	X	X

Abbreviations: CBC = complete blood count; D = day; EOT = end of treatment; LDH = lactate dehydrogenase; MRD = minimal residual disease; PK = pharmacokinetic(s); PRO = patient-reported outcome; Q4W = every 4 weeks; WBC = white blood cell.

- a Screening pregnancy test may be used if performed within 72 hours of first dose; pregnancy tests will be conducted once every month; additional guidance is provided in Section 5.1.1.
- b If magrolimab and azacitidine are administered on the same day, only one such study assessment is needed. Assessments should be performed prior to study treatment administration. For monitoring of infusion-related reactions, please refer to Section 6.5

- c Pretreatment assessments for the initial dose may be collected up to 72 hours before administration of study treatment; thereafter, pretreatment assessments are to be collected within 24 hours prior to study treatment administration.
- d Additional samples for CBC may be collected outside of the protocol-specified time points to ensure a WBC level $\leq 20 \times 10^3/\mu\text{L}$ prior to each magrolimab/placebo dose during the first 28 days of magrolimab priming dose. Peripheral blasts should be included in the CBC assessments.
- e Hemoglobin must be checked again 3 to 6 hours after the initiation of the first and second doses of magrolimab/placebo during initial treatment. The participant should be transfused as clinically appropriate. Investigators should consider additional hemoglobin monitoring during the first week of treatment in participants with symptoms of anemia or increased risk for complications of anemia.
- f Peripheral smears will be collected predose and assessed locally.
- g Samples for PK and biomarker studies will be collected predose within 12 hours prior to study treatment administration.
- h Samples will be collected prior to first maintenance dose (Day 57), ninth (Day 169) maintenance dose, and EOT.
- i Samples will be collected predose on Day 57, Day 113, Day 169, Day 253, Day 337, and EOT.
- j When collected on the day of study treatment dosing, the blood sample for antidrug antibodies must be collected at the same time as the predose PK sample.
- k Vital signs will be assessed prior to infusion/injection of each study treatment. Weight will be assessed every 4 weeks. Details are provided in Section 5.1.5.
- l Premedication is required prior to the administration of the first 4 doses of study treatment and in case of reintroduction with repriming. Premedication for subsequent treatment periods may be continued based on the treating physician's clinical judgment and the presence/severity of prior infusion-related reactions. In the case of a Grade 3 infusion-related reaction, a premedication regimen for subsequent treatment periods is required (Section 6.5).
- m Magrolimab or saline placebo should not be given on consecutive days. The duration of each magrolimab/placebo infusion including flush will be 3 hours (± 30 minutes) for the first 3 doses of treatment, and then 2 hours (± 30 minutes) for infusions beyond the first 3 doses. All participants should be monitored for 1 hour after infusion for doses during the first 28 days and the repriming doses.
- n Within 24 hours prior to each of the first 2 doses of magrolimab/placebo infusion, all participants must have a documented hemoglobin ≥ 9 g/dL. Participants who do not meet these criteria must be transfused and have their hemoglobin rechecked to meet the minimum hemoglobin threshold prior to administering each of the first 2 doses of magrolimab/placebo.

Table 5. Schedule of Assessments - Posttreatment

Visit Window	End-of-treatment Visit	Safety Follow-up Visit/Call (Telephone) ^a		Long-term Follow-up	Survival Follow-up
	Within 7 Days after Last Dose or EOT Decision	30 Days after Last Dose	70 Days after Last Dose ^k	Until Start of New Anticancer Therapy or Transformation to AML ^b	Every 2 Months Until Death or End of Study
	± 7 Days	± 7 Days	± 7 Days	+4 Weeks	
Serum or urine pregnancy test	X			Q4W ^c	Q4W ^c
CBC with differential, platelet count, reticulocytes	X			Q8W ^d	
Serum or plasma chemistry	X				
Peripheral blood for biomarker studies	X				
Pharmacokinetics	X				
Antidrug antibodies	X				
Bone marrow biopsy and aspirate for MRD monitoring and cytogenetics ^{d,e}	X			Q8W ^d	
Response assessment ^{e,f}	X			Q8W ^d	
ECOG	X				
Vital signs	X				
Symptom-directed physical examination	X				
PRO assessment ^g	X			X	
Adverse events ^h	X	X	X		
Concomitant medications	X	X	X		
Blood transfusion ⁱ				X	X
New anticancer therapy ^j				X	X
Survival follow-up					Q2M

Abbreviations: AE = adverse event; AML = acute myeloid leukemia; CBC = complete blood count; CR = complete remission; eCRF = electronic case report form; EOT = end of treatment; EQ-5D-5L = 5-level EuroQol 5 dimensions; FACT-Anemia = Functional Assessment of Cancer Therapy-Anemia; IWG = International Working Group;

MDS = myelodysplastic syndrome; MRD = minimal residual disease; PGIC = Patient Global Impression of Change; PGIS = Patient Global Impression of Severity; PR = partial remission; PRO = patient-reported outcome; QxM = every x months; QxW = every x weeks; SAE = serious adverse event.

- a If the participant experiences a treatment-related AE or an SAE (regardless of attribution), the participant must be asked to come to the site.
- b Until start of new anticancer therapy or transformation to AML, whichever comes first.
- c Collect until the end of the contraception requirement.
- d Bone marrow assessment, MRD, CBC, and response assessment should be performed until start of new anticancer therapy or transformation to AML, whichever comes first. Conventional cytogenetic testing (per institutional standards) is required for all participants.
- e For participants who come off the study treatment to undergo a stem cell transplant, response assessments for relapse/remission status and bone marrow aspirate results are required to be obtained locally and entered into the eCRF.
- f Response assessment at EOT visit not required if performed within the last 30 days or progressive disease has been documented. After disease progression (including treatment failure by IWG criteria and relapse after CR or PR), response assessment will focus on evaluation of transformation to AML.
- g Paper PROs will be administered in this study: The FACT-Anemia questionnaire, the EQ-5D-5L, the PGIS, and the PGIC will be administered. The participant should complete these questionnaires before other study procedures at required visits. FACT-Anemia and EQ-5D-5L should be implemented prior to PGIS/PGIC. FACT-Anemia, EQ-5D-5L, the PGIS, and the PGIC should also be collected during long-term follow-up prior to initiation disease progression or initiation of a new anticancer therapy.
- h Report all AEs through the Safety Follow-up Visit/Call and any treatment-related SAEs thereafter.
- i Collect blood transfusions until start of new anticancer therapy.
- j Collect new anticancer therapy data following the last dose of study treatment.
- k For participants who do not initiate new anticancer therapy after the last dose. See Section [5.1.10](#) for adverse event reporting details.

Table 6. Schedule of Assessments - Repriming (Required After > 4 Weeks Have Lapsed Since the Last Dose of Magrolimab/Placebo Delays)

Visit Window (Days)	Day										
	1	2	3	4	5	6	7	8	11	15	22
	-	-	± 3	± 3	± 3	± 3	± 3	± 3	± 3	± 3	± 3
Pregnancy test	X										
CBC with differential, platelets, and reticulocytes ^{a,b}	X	X		X				X	X	X	X
Haptoglobin and LDH	X							X			
Serum or plasma chemistry ^a	X							X		X	X
Peripheral smear ^{a,c}	X	X							X		
Peripheral blood for biomarker studies ^d	X							X			
PK ^d	X							X			
Antidrug antibodies ^a	X										
Vital signs ^c	X	X						X		X	X
Symptom-directed physical examination ^a	X							X		X	
Adverse events	X	X	X	X	X	X	X	X	X	X	X
Concomitant medications	X	X	X	X	X	X	X	X	X	X	X
Blood transfusions	X	X	X	X	X	X	X	X	X	X	X
Premedication ^f	X			X				X	X		
Magrolimab/placebo: repriming ^g	X			X				X	X	X	X

Abbreviations: CBC = complete blood count; ECOG = Eastern Cooperative Oncology Group; LDH = lactate dehydrogenase; PK = pharmacokinetic(s); PRO = patient-reported outcome; WBC = white blood cell.

a Pretreatment assessments are to be collected within 24 hours prior to study treatment administration.

